## 2. BACKGROUND

ASD is a heterogeneous neurodevelopmental disorder often with life-long consequences that affects young children during critical times in their development. The latest estimates from the Center for Disease Control estimates an ASD affects as many as 17 per 1000 children (1 in 59) in the United States with recently estimation demonstrating that the prevalence continues to rise. ASD is defined by impairments in social communication as well as the presence of restrictive interests and repetitive behaviors. ASD is frequently associated with co-occurring problems such as gastrointestinal abnormalities, seizures, attention deficits, anxiety and allergies - to name a few.

Full Study Title: Effect of a Wide Spectrum Nutritional Supplement on Mitochondrial Function in Children with Autism Spectrum Disorder (ASD)

Principal Investigator: [name]; Co-Investigators: [name]

Sponsor: [name]; IND 142751; ClinicalTrials.gov ID: NCT03835117; Protocol Version 02/11/2022

Funding Source: Turnabout for Autism (Private Foundation), Pleasanton CA.

Despite the fact that the prevalence of ASD has dramatically increased over the past two decades, there currently is no effective medical treatment for children with ASD. A recent multicenter study showed that optimal outcomes can be achieved in a subset of ASD children. Moreover, a study that analyzed the annual change in ASD symptoms in 6,975 children showed that some children with ASD can substantially improve. However, these studies did not address whether particular therapies were associated with better outcomes. In addition, the findings suggest that only a minority of children with ASD show substantial improvement over time, underscoring the need for more effective treatments.

Currently the only well-accepted treatment for **core** ASD symptoms is behavior therapy such as Applied Behavioral Analysis (ABA) and Early Intensive Behavioral Intervention. However, such therapy requires near full-time engagement with a one-on-one therapist over several years. The evidence for early intervention rests primarily on single-subject design studies with few randomized controlled studies and these interventions rarely result in complete recovery. Moreover, access to such intensive treatments is often limited and may only be available in highly specialized centers. Behavior therapy is inconsistently covered by medical insurance and not uniformly available in the education system. Thus, the *de facto* standard-of-care for treating ASD is a combination of educational and allied health therapies (speech and occupational therapies) in various settings. Although these interventions may promote development in children with ASD, they may not address the underlying pathophysiological abnormalities in ASD. Most individuals with ASD require life-long supportive care and do not achieve independent living in adulthood.

Evidence-based medical treatments for ASD are limited. There is no United States (US) Food and Drug Administration (FDA) approved medical therapy that addresses **core** ASD symptoms or the pathophysiological processes that underlie ASD. The two FDA approved drugs, both atypical antipsychotics, are indicated for serious behavioral problems in children with ASD. Although these drugs, risperidone and aripiprazole, may improve social interactions as a secondary benefit, the detrimental effects on lipid and glucose metabolism and body weight are well established and may develop quickly (within 12 weeks). These metabolic changes increase the risk of cardiovascular disease and type-2 diabetes. Although the incidence is low, tardive dyskinesia, a potentially permanent movement disorder, is an additional risk. Thus, there is a pressing need for safe medications that affect target pathophysiological processes and treat core ASD symptoms.

Several medications are used off-label to treat associated, but not core, ASD symptoms. These medications do not address underlying pathophysiological abnormalities. A systematic review of attention-deficit hyperactivity disorder (ADHD) treatments for ASD highlights the complicated nature of medication treatment due to the diverse nature of children with ASD and associated adverse effects (AEs). A recent Cochrane review found no evidence for efficacy of selective serotonin reuptake inhibitors in ASD. Although studies show positive effects of methylphenidate and extended-release guanfacine on hyperactivity, these medications did not improve core features of ASD and the AE burden was higher than found in children with ADHD. Pharmaceutical companies have developed medications targeting excitatory-inhibitory neurotransmission imbalances identified in animal models of ASD, but the first of these compounds failed to demonstrate efficacy in a double-blind placebo-controlled (DBPC) trial, leading to termination of the research program.

### **3. An Integrated Approach to Understanding Autism Spectrum Disorder**

Our novel approach to treating ASD is to address the underlying physiological abnormalities associated with ASD as we hypothesize that these physiological abnormalities are driving abnormal behavior and cognition. Of note, ASD is associated with physiological disturbances including abnormal redox and mitochondrial metabolism. In fact, between 5%-80% of children with ASD demonstrate evidence of mitochondrial dysfunction and 5% of children with ASD appear to have

Full Study Title: Effect of a Wide Spectrum Nutritional Supplement on Mitochondrial Function in Children with Autism Spectrum Disorder (ASD)

Principal Investigator: [name]; Co-Investigators: [name]

Sponsor: [name]; IND 142751; ClinicalTrials.gov ID: NCT03835117; Protocol Version 02/11/2022

Funding Source: Turnabout for Autism (Private Foundation), Pleasanton CA.

mitochondrial disease. This is in comparison to the general population where mitochondrial disease is believed to affect less than 0.1% of the population.

Repeated studies have suggested that genetic defects are found only in a minority of children with ASD, including a minority of children with ASD with mitochondrial disease and many case reports and series have described only moderate, rather than severe, deficiencies in the electron transport chain (ETC) activity in those with ASD and mitochondrial disease. Perhaps more striking is the fact that ETC activity in muscle, skin, buccal epithelium and brain has been documented to be significantly increased, rather than decreased, in some individuals with ASD. This is consistent with our *in vitro* data showing elevated mitochondrial activity in lymphoblastoid cell lines (LCLs) derived from children with ASD. We recently demonstrated that this alteration in mitochondrial function is associated with more severe repetitive behaviors. Thus, the current data points to possible non-genetic defects or changes causing abnormal mitochondrial function as well as unique types of mitochondrial dysfunction in individuals with ASD.

Mitochondrial dysfunction has profound significance for health. Mitochondria are essential for a wide range of functions in almost every cell in our body. Best known for their role in the production of adenosine triphosphate (ATP), mitochondria are also intimately involved in other essential cellular functions such as calcium buffering, redox regulation, apoptosis and inflammation and have a role in non-energy producing metabolic pathways, such as the urea cycle and porphyrin pathway. Additionally, ATP produced by the mitochondria is essential for many cellular systems. Thus, abnormal mitochondrial function can adversely affect a wide range of cellular systems. Mitochondrial dysfunction is recognized to contribute to the pathophysiology of many common diseases, especially those thought to have a substantial environmental component, including psychiatric diseases, neurodegenerative disorders, persistent systemic inflammation, cardiac disease, cancer and diabetes. Abnormalities in mitochondrial function are closely associated with neurodevelopmental disorders, including genetic syndromes closely associated with ASD including phosphatase and tensin homolog (PTEN) and WDR45 mutations, septo-optic dysplasia and Rett, Phelan-McDermid, 15q11-q13 duplication, Angelman and Down syndrome.

Most significantly, there is evidence that nutritional supplement used in children with ASD target the mitochondrial. Several studies have demonstrated that nutritional supplements, such as carnitine, nicotinamide adenine dinucleotide (NAD), ubiquinol and ubiquinone designed to treat individuals with mitochondrial disease may be helpful in children with ASD. Two DBPC studies demonstrated improvement in ASD symptoms with carnitine supplementation with some improvements directly related to the change in blood carnitine levels. In another study, NAD and ribose appeared to improve metabolic biomarkers in children with ASD and symptoms of mitochondrial dysfunction. Two studies have reported behavioral improvements in children with ASD using ubiquinol and ubiquinone. While these aforementioned studies did not specifically target individuals with mitochondrial dysfunction, one recent study examined the behavioral effects of a customized mitochondrial supplement in ASD children with mitochondrial dysfunction. Legido et al in an open-label study treated 11 children with ASD and abnormal Complex 1 and/or Complex 4 activity, as measured by the buccal swab method, with a mitochondrial cocktail containing carnitine, coenzyme Q10 and alpha-lipoic acid. Three months of treatment improved the index of mitochondrial function and improved several behavior scales including lethargy and inappropriate speech subscales from the Aberrant Behavior Checklist (ABC). Three months after withdrawal of the treatment the lethargy and inappropriate speech subscales significantly worsened.

Thus, we aim to build on this previous evidence in order to demonstrate that a mitochondrial targeted nutritional supplement commonly given to children with ASD indeed positively affect mitochondrial

Full Study Title: Effect of a Wide Spectrum Nutritional Supplement on Mitochondrial Function in Children with Autism Spectrum Disorder (ASD)

Principal Investigator: [name]; Co-Investigators: [name]

Sponsor: [name]; IND 142751; ClinicalTrials.gov ID: NCT03835117; Protocol Version 02/11/2022

Funding Source: Turnabout for Autism (Private Foundation), Pleasanton CA.

function. Previous studies have been low quality because they were either open-label or did not measure physiological response of the treatment. We wish to perform a rigorous study that targets the subset of children with ASD with abnormal variations in mitochondrial function associated with ASD in order to increase the scientific evidence to understand how the physiological mechanisms which nutritional supplements may affect children with ASD.

#### **4. SPECIFIC AIMS**

**Primary Aim: To determine if a wide-spectrum nutritional supplement can influence**

**mitochondrial activity in 50 individuals with ASD and signs and symptoms of abnormal**

**mitochondrial function.** The trial design will be a 24-week randomized, DBPC cross-over study.

We hypothesize that the supplement will result in a greater ability to normalize mitochondrial activity as compared to placebo. To test this hypothesis we will:

- a. Test mitochondrial activity at baseline and after the placebo and supplement arms of the study and determine if the nutritional supplement normalizes mitochondrial activity significantly more than placebo.
- b. Test redox metabolism at baseline and after the placebo and supplement arms of the study and determine if the nutritional supplement improves redox metabolism significantly more than placebo.
- c. To determine if specific biomarkers (Folate Receptor Autoantibody, Single Nucleotide Polymorphism) can predict response to treatment.

**Secondary Aim: To evaluate the effectiveness of a wide-spectrum metabolic supplement on core**

**and associated ASD symptoms.** We will determine if symptoms associated with ASD will be effected by a nutritional supplement which targets normalizing mitochondrial function. We will evaluate:

- a. Core ASD symptoms as measured by the Childhood Autism Rating Scale (CARS).
- b. Clinical Global Impression Severity and Improvement
- c. Behavior, including repetitive behavior Children Yale Brown Obsessive Compulsive Scales Modified for ASD (CYBOCS-ASD), Irritability, Social Withdrawal, and Hyperactivity subscales of the Aberrant Behavior Checklist (ABC), Parent-rated Anxiety Scale-ASD (PRAS-ASD), Caregiver Strain Questionnaire (CGSQ), Parent Targeted Problems and adaptive behavior (Vineland III).
- d. Somatic manifestations of pain, fatigue and gastrointestinal symptoms

**Tertiary Aim: To collect samples which will allow the evaluation of the effect of a wide-**

**spectrum metabolic supplement on changes in cellular regulation and to determine if**

**specific gene abnormalities or cellular regulatory factors or autoantibodies results in**

**abnormal mitochondrial function.** In the future we wish to determine the changes in cellular

regulation as a result of the treatment by examining several aspects of cellular regulatory elements. We also wish to determine if certain genetic or epigenetic changes are associated with mitochondrial dysfunction in ASD. The current funding does not allow these advanced analysis to be performed at this time but we will collect samples so these studies can be performed in the future. In the future we will examine:

- a. Gene expression by measuring RNA expression
- b. Cellular regulation by measuring microRNA expression
- c. Concentrations of key regulatory proteins
- d. Methylation of targeted genes
- e. Abnormal gene sequences (mutations, rare polymorphisms)
- f. Autoantibodies to Brain tissue and the folate receptor alpha

Full Study Title: Effect of a Wide Spectrum Nutritional Supplement on Mitochondrial Function in Children with Autism Spectrum Disorder (ASD)

Principal Investigator: [name]; Co-Investigators: [name]

Sponsor: [name]; IND 142751; ClinicalTrials.gov ID: NCT03835117; Protocol Version 02/11/2022

Funding Source: Turnabout for Autism (Private Foundation), Pleasanton CA.

## 5. RESEARCH PLAN

### Trial Design

50 children with ASD and signs and symptoms of abnormal mitochondrial activity will be randomized in 1:1 ratio to receive a wide-spectrum nutritional supplement that targets mitochondrial function or placebo for 12 weeks under DBPC conditions. Each participant will serve as their own control in the cross-over design. Using a phone screen, we will identify children (age  $\geq$  2:6 and  $<$  17:3) with a diagnosis of ASD and evidence of mitochondrial function which is significantly higher or lower than average (here forth referred to as mitochondrial dysfunction). Children with suspicion of mitochondrial dysfunction will be invited to participate in a screening visit to make sure they meet including and exclusion criteria. If the screening visit is longer than 6 weeks from the prescreening, we will repeat the baseline metabolic testing to ensure an accurate baseline mitochondrial measurement. If they meet criteria, the baseline visit will be completed within 2 week but we will attempt to complete it on the same day (Table 1). Upon successful completion of the baseline visit, the participant will enter Phase 1 of the trial and will be randomized to receive active treatment or placebo for 12 weeks under DBPC conditions. At the end of the 12 weeks (end of Phase 1), the participant will return for evaluations similar to the ones conducted at baseline. Upon successful completion of the post-Phase 1 visit, the participant will start Phase 2 where they will receive active treatment or placebo, depending on what they received during Phase 1 – they will be crossed over to the opposite treatment regimen. Potential AEs, compliance and concomitant treatments will be monitored every four weeks.

### Inclusion criteria

- Boys and girls  $\geq$  2 years 6 months of age to  $<$  17 years 3 months of age;
- Weight  $\geq$  15 kg and  $\leq$  100kg;
- DSM-5 diagnosis of *Autism Spectrum Disorder* as established by formal clinical assessment which includes a gold-standard tool such as the Autism Diagnostic Observational Schedule.
- Current Childhood Autism Rating Scale, 2nd Edition (CARS-2) score meeting criteria for Autism Spectrum Disorder (Standard Form, cutoff  $\geq$  30 for children  $<$  13 years of age;  $\geq$  28 for children  $\geq$  13 years of age; High Functioning Form, cutoff  $\geq$  28)
- IQ at least 30 as measured by the Differential Abilities Scale (DAS)
- Stable educational and therapy plan (one month) with no **planned** changes in the intensity of treatment for 12 weeks.
- English spoken in the home and at least one parent is able to read, write and speak English.
- Stable medication (no changes in past 6 weeks) and no **planned** changes for the study duration.
- Signs and symptoms of mitochondrial dysfunction (See Figure Below)

Full Study Title: Effect of a Wide Spectrum Nutritional Supplement on Mitochondrial Function in Children with Autism Spectrum Disorder (ASD)

Principal Investigator: [name]; Co-Investigators: [name]

Sponsor: [name]; IND 142751; ClinicalTrials.gov ID: NCT03835117; Protocol Version 02/11/2022

Funding Source: Turnabout for Autism (Private Foundation), Pleasanton CA.

### Clinical Abnormalities Found in Mitochondrial Disease

Not Typically Clinically Abnormal in ASD	Clinically Abnormal in Some ASD Individuals
Ophthalmoplegia	Stroke-like episodes
Facies myopathica	Migraine
Hematology, Vision	Cortical blindness
Hearing, Brainstem abnormalities	Development Delay
	Loss of Skills
	Seizures
	Muscle Weakness
	Peripheral Neuropathy
	Abnormalities in Endocrine/Growth, Gastrointestinal System, Lactate, Pyruvate, Alanine

### Exclusion criteria

- IQ below 30 as measured by the Differential Abilities Scale (DAS)
- Presence of serious behavioral problems (tantrums, aggression, self-injury) for which another treatment is warranted.
- Significant medical condition by history or by physical examination or lab tests that would be incompatible with the treatment.
- Children taking anticonvulsant medication for seizures or active epilepsy.
- Diagnosis of Mitochondrial Disease
- Current use of SpectrumNeeds or QNeeds

### Procedures

Randomization: Randomization will be carried out within site using permuted blocks of 4 subjects without additional stratification to nutritional supplement or placebo in a 1:1 ratio. Statisticians will prepare the permuted blocks for each site and will be sent to the Investigational Pharmacist at each site. Investigators and study staff will be blind to the allocation sequence.

**Compensation** Participants will be compensated \$50 for each of the four physical visits.

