Full Study Title: Effect of a Wide Spectrum Nutritional Supplement on Mitochondrial Function in Children with Autism Spectrum Disorder (ASD)

Principal Investigator: [name]; Co-Investigators: [name]

Sponsor: [name]; IND 142751; ClinicalTrials.gov ID: NCT03835117; Protocol Version 02/11/2022

Funding Source: Turnabout for Autism (Private Foundation), Pleasanton CA.

	Synopsis
Protocol Title	Effect of a Wide Spectrum Nutritional Supplement on Mitochondrial Function in Children with Autism Spectrum Disorder (ASD)
IRB	WCG Institutional Review Board
Protocol Ver	Wednesday, August 3, 2022
Sponsor	[name], Rossignol Medical Center, Phoenix AZ
IND # / FDA	IND 142751; FDA Division of Psychiatry; Protocol Version 1.4
NCT ID	NCT03835117
Principal Investigator	[name], PhD, Rossignol Medical Center, [name]
Site- Investigator	[name], Southwestern Autism Resource and Research Center (SARRC), Phoenix AZ
Co-Investigators	1. [name], Director of CNNH NeuroGenomics Program, Center for Neurological and Neurodevelopment Health, Voorhees, NJ. 2. [name] D.O. (SARRC), Phoenix AZ
Clinical Sites	1. SARRC, Phoenix, AZ
Laboratory Sites	1. Laboratory of [name], State University of New York Downstate—[name] 2. Religen Inc, Plymouth Meeting, PA 3. Laboratory of [name], Icahn School of Medicine at Mount Sinai, NY NY 4. Laboratory of [name] at the University of Oklahoma Health Sciences Center in Oklahoma City, OK 5. 3billion Laboratory in Seoul, South Korea 6. Iliad Inc, Plymouth Meeting, PA
Study Design	Prospective Randomized 24-week Double-Blind Placebo-Controlled Cross-over
Objectives	To evaluate the metabolic effects of a comprehensive wide-spectrum supplement for children with ASD to determine whether it physiologically targets mitochondrial pathways known to be abnormal in children with ASD.
Participants	Up to 50 children, aged 2 years 6 months to 17 years 3 months with confirmed ASD and mitochondrial dysfunction. Participants will have moderate disease severity (clinic global impression of 4 or above) and stable behavioral, education and medical treatment. Those with severe intellectual impairment, disruptive behavior or medical conditions such as epilepsy will be excluded.

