The nutritional supplement used will be a combination of SpectrumNeeds and QNeeds, both produced by NeuroNeeds (Old Lyme, CT; See Table 1). Weight based dosing will be used. The daily serving size will be divided into two daily doses in the form of a powder which can be mixed into liquid or food. Together, there are 34 different dietary supplements in the products. Thirty-two of the 34 supplements do not exceed the Tolerable Upper Intake Limits set by the United States Institute of Medicine. The exceptions are:

1. The niacin dosing is about the upper limit. Niacin in the form of nicotinic acid is well known for causing benign flushing. Niacinamide (also known as nicotinamide) is the form of niacin in SpectrumNeeds, and this form does not cause flushing.
2. Folate exceeds the upper limit. It should be noted that half of the total folate provided is in the form of Quatrefolic™ (6S)-5-Methyltetrahydrofolic acid Glucosamine salt (55% FOLATE), which is microbial sourced, not synthetic. There is no known upper tolerable limit for non-synthetic folate, only for synthetic folate. The other half is in the form of calcium folinate. Dosage of folate used in this supplement are about one-half that commonly recommended during pregnancy to women with a prior child with a neural tube defect who may get pregnant. Dosages of folinate are one half to one-twenty-fifth the dosing commonly recommended in children with ASD. These dosages are known to be generally well tolerated in ASD children.

Except for ubiquinol, all of these nutrients are provided in a powder form in SpectrumNeeds. The physical stability and bioavailability of ubiquinol is insufficient in powder form, and thus ubiquinol is provided separately in QNeeds gel capsules. These capsules can be swallowed whole, or cut with scissors and the contents squeezed out and added to SpectrumNeeds just before ingestion.

Placebos will have the same look, feel and taste as the active treatments. For example, the SpectrumNeeds is a silica powder flavored by monk fruit extract, so the inert silica powder with the same flavoring will be used as a control. Similarly, in QNeeds, the ubiquinol is carried by purified water and glycerin colored by caramel liquid, so for the placebo the same carrier and color will be used in the gel capsule without ubiquinol.

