## **Potential Risks**

The risks associated with these procedures include exposure to the study supplement or placebo, and the risk associated with venipuncture. The blood draws poses a possible risk of bruising at the site of the draw, light-headedness and fainting along with a remote chance of infection.

Although highly unlikely, there are potential privacy risks associated with participating in such a study. There is minimal risk associated with the completion of rating scales and assessment measures. Blood draws are common procedures and will be performed by a certified phlebotomist. We will offer a numbing cream prior to the blood drawing procedure. We will systematically review adverse at follow up phone calls and clinic visits (see below). Parents will be given phone numbers of the principal investigator and study physician – who will be available after hours. The PI and study physician have access to the pharmacy after hours – if it is necessary to break the blind.

The nutritional supplement and supplements similar to it have been on the market and used widely in the autism community. There have been few reported side effects of this supplement. They include nausea and hyperactivity, both of which resolve on their own. One similar supplement produced by [name] at Arizona State University has been studied in three clinical trials without reported significant adverse effects. In addition, the majority of the ingredients in the nutritional supplement are well within the proposed upper tolerable limits recommended by the institute of medicine and the two vitamins that exceed these limits are known to be well tolerated at doses well above the recommend upper limits. Increased consumption of B vitamins may also temporarily change urine color.

Confidentiality will be maintained throughout the project period. With the exception of tests that require date of birth, research records will not include names or contact information. Subjects will be identified only by their code numbers. A file with personal health information (e.g., names and addresses) will be kept separately in a locked file cabinet.

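### The protocol prints a fixed block size of 4 for an unstratified, single-site list, so a few known sequences can give away others: a minor, secondary threat to the rated outcomes

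*Combined protocol and SAP*

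**What the plan says.** The randomisation paragraph in Section 5 (Procedures) reads: "Randomization will be carried out within site using permuted blocks of 4 subjects without additional stratification". It mentions no variation in block size. The list goes to the pharmacy: "Statisticians will prepare the permuted blocks for each site and will be sent to the Investigational Pharmacist at each site". Concealment is stated as "Investigators and study staff will be blind to the allocation sequence". Under Trial Design, "50 children with ASD and signs and symptoms of abnormal mitochondrial activity will be randomized in 1:1 ratio", and each child later switches to the other product. The randomisation text speaks of several sites, but the clinical-site entry in the Synopsis is only "1. SARRC, Phoenix, AZ".

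On masking, Section 5 (Investigational Product) says "Placebos will have the same look, feel and taste as the active treatments" and describes the powder placebo: "so the inert silica powder with the same flavoring will be used as a control". No match for urine colour is described. Section 7 (Potential Risks) notes: "Increased consumption of B vitamins may also temporarily change urine color". The same section lets the principal investigator and study physician reach the pharmacy after hours if the blind must be broken. No check of the blind is described.

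**The concern.** A block of 4 under 1:1 allocation always holds two children per sequence. With one site and no strata, enrolment order should equal list order, so the block boundaries are known to anyone who holds the protocol and counts. Sequences learned for some children then carry information about others in the same block. Because the design has only two sequences, one deduced label covers both 12-week phases.

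The protocol itself names two ways in which a sequence might be learned: the possible urine-colour change, which the described placebo does not mimic, and an emergency code break. The adverse-event review at each visit also asks about bladder function (Section 7, Monitoring for Adverse Events), so such a report could reach the treating clinician.

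The stake is rating bias on clinical outcomes. The OACIS is scored by the study physician with no stated shielding from adverse events. The descriptions of the CARS and CYBOCS-ASD state no blinding of the rater.

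**Working it through.** **The plan's own figure.** The plan gives no figure for predictability. Its only design figure is 80% power for effect size 0.5 at alpha 0.01. A two-sided paired t-test with n = 50, with the effect size taken on the paired difference, gives 79.9%, so that figure reproduces. Nothing below depends on it.

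**Inputs.** From the protocol: block size 4, 1:1, no strata, one listed site, 50 children (50 = 12 × 4 + 2). Assumed: children are randomised in enrolment order and the observer knows that order. The documents give no frequency for correct readings, so that share (q) is also assumed.

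**Within one block (6 equally likely arrangements of 2 + 2).**
- One sequence known: nothing else is certain.
- Two known: the other two are certain only if the two match, which has probability 1/3.
- Three known: the fourth is always certain.

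**All earlier sequences known (worst case).**
- Certain before assignment: 8 of 24 positions over the 6 arrangements, or 8/6 = 1.33 per block. Over 12 full blocks this is 12 × 1.33 = 16 of 50 (32%). The last two children are never certain.
- Correct best guesses: 17 of 24, or 17/6 = 2.83 per block. Over the whole list: 12 × 2.83 + 1/2 + 2/3 = 35.2 of 50, against 25 with no block knowledge.

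**Only a share q of children read, every reading assumed correct.** An unread child is certain when both children on the opposite sequence in its block have been read, which has probability q². The expected number of extra children deduced among the 48 in full blocks is 48(1 − q)q².

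| q (assumed) | q² | Extra children deduced, of 48 | Correct guesses without block knowledge, (1 + q)/2 | Correct guesses with fixed 4 |
|---|---|---|---|---|
| 0.3 | 9% | 3.0 | 65% | 73% |
| 0.5 | 25% | 6.0 | 75% | 84% |
| 0.7 | 49% | 7.1 | 85% | 93% |

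The last column is worked here for q = 0.5. Let i be the number read of the one other child on the unread child's own sequence, and j the number read of the two on the opposite sequence. The guess is right if j > i and a coin toss if j = i. P(j > i) = 0.5 × 0.75 + 0.5 × 0.25 = 0.50. P(j = i) = 0.5 × 0.25 + 0.5 × 0.50 = 0.375. So an unread child is guessed correctly with probability 0.50 + 0.1875 = 0.6875, and overall 0.5 + 0.5 × 0.6875 = 0.844.

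**After varying the block size** (simulation with sizes 4 and 6 chosen at random, the set of sizes known to the observer but not their order).
- All earlier sequences known: certain assignments fall from 16.0 to 2.7–2.8 of 50 across runs. Correct best guesses fall from 35.2 to 34.4–34.5 of 50.
- Partial readings over all 50 children: unread children deduced with certainty fall from 9% to 0.3%, 24% to 3% and 47% to 16% at q = 0.3, 0.5 and 0.7. (The 24% and 47% are q² × 48/50.) Overall correct guesses fall from 73%, 84% and 93% to 71%, 82% and 91%.

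**Balance.** At 50 children a fixed-4 list stops two children into a block, so the worst split is 26/24. With sizes 4 and 6 the list stops at the end of a block, or two children into a block of 4, or two or four into a block of 6. The worst excess is again 2, giving 26/24.

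**The case against.** The case against giving this much weight is strong on several counts.

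- **The cue works without the blocks.** In a cross-over, a child's own change in urine colour between phases can reveal that child's order directly. Block size only extends what has already leaked. This stands.
- **The remedy leaves most of the guessing advantage.** It removes most certain deductions but moves best-guess accuracy by only about two percentage points, and rating bias does not require certainty. This stands.
- **Safeguards exist.** The CGI-I rater is to be blind to assignment, adverse events and dose. The CGI-S rater is blind to assignment, and the parent target narratives go to a blinded panel. Mitochondrial function is assayed from buccal swabs. This stands, and it narrows the exposure. It does not cover the OACIS, CARS or CYBOCS-ASD, and shielding a rater from one child's adverse events does not prevent inference from other children's sequences.
- **The cue is tentative.** The protocol calls the colour change possible and temporary, and nothing shows that raters see it. This stands for urine colour; a code break would be a sure reading.

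A reader might go further and infer that the promise to keep staff blind to the sequence cannot hold. The documents do not support that. The sentence governs access to the list, and possible inference after unmasking does not contradict it. The 16-of-50 figure also presupposes that all earlier sequences are known, in which case the blind has already largely failed.

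**Conclusion.** The point holds as a minor weakness in the design. A fixed, printed block of 4 at a single listed site allows deductions that varying, undisclosed sizes would mostly prevent. At worst 16 of 50 assignments are predictable with certainty. With partial and correct readings, 9% to 49% of unread children in full blocks become certain as q runs from 0.3 to 0.7. These figures rest on a known enrolment order, correct readings and, for the partial case, an assumed q.

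Two stronger conclusions should not be drawn. The documents do not show that the rater blind is broken: rating bias is a plausible inference, most plausible for the OACIS and then for the CARS and CYBOCS-ASD. Nor do they show that the mitochondrial outcome is affected, since it is a laboratory measurement and each child is compared with itself.

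**What to change.** In Section 5 (Procedures), replace the fixed block of 4 with permuted blocks of randomly varying size and do not state the sizes. Sizes 4 and 6 in random order would serve. Record them only in the restricted randomisation file kept by the statistician who prepares the list and the investigational pharmacist. If enrolment has begun, apply this to the part of the list not yet allocated; it cannot protect children already allocated under the known size. In the same edit, reconcile the references to several sites with the single clinical site in the Synopsis.

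The cost is a regenerated list and a short protocol amendment, with no loss of balance at 50 children. The change does not deal with the urine-colour cue, which would still act on each child directly.
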